#### *Outcome measurements:*

*Weight:* We will compare the duration and magnitude of weight loss among exenatide responders with the

duration and magnitude of weight loss among subjects assigned to placebo with a calorie-restricted diet over 52 weeks. We will also compare changes in weight at 3 and 6 months after the cessation of exenatide treatment or diet. Weight loss will be correlated to baseline BMI.

**Body composition:** Baseline body composition may predict response to exenatide treatment, and weight loss with exenatide may be associated with decreased fat versus lean body mass compared to diet-induced weight loss. We will compare the effect of exenatide treatment versus caloric reduction on body composition over 52 weeks using bioelectrical impedance analysis (BIA) and by measuring waist circumference.

**Resting energy expenditure (REE):** Our initial data suggest that exenatide may blunt the decrease in resting energy expenditure that is typically associated with diet-induced weight loss. We will measure resting energy expenditure (REE) via indirect calorimetry at baseline, at weeks 12, 24, and 52, and after 5%, 10%, 15% weight loss is achieved, and at additional 5% weight loss timepoints, as applicable (i.e., 20%, 25%, etc).

**Mixed meal test:** Exenatide may improve beta cell function and lower postprandial triglycerides in nondiabetic individuals. Measurement of fasting insulin and triglyceride levels does not capture these effects. We will administer a mixed liquid meal (Boost) and measure serial postprandial insulin, , and triglyceride levels. Subjects will have a mixed meal test at baseline, and at weeks 12, 24, and 52.

**Thermic effect of food:** Exenatide treatment may result in an increase in the thermic effect of food, which could explain, at least in part, why we did not see a significant reduction in energy expenditure among exenatide high responders in our initial study. We will measure the thermic effect of food using indirect calorimetry following the mixed meal challenge. Energy expenditure will be measured for 15-20 minutes every hour for four hours after the mixed meal challenge. The thermic effect of food will be measured in a subset of subjects at baseline, and at weeks 12, 24, and 52.

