**Serum metabolic parameters:** Subjects will have blood drawn to measure leptin, soluble leptin receptor, insulin, cortisol, adiponectin, CRP, and FGF21. Blood will also be banked to measure other metabolic parameters in the future. Serum metabolic parameters will be measured at baseline and at weeks 12, 24, and 52. Serum metabolic parameters will also be measured when weight loss at a 5% increment has been achieved, or upon study completion if weight loss targets are not achieved.

**Hunger/Nausea/Satiety visual analog scales (VAS):** Perceptions of hunger, nausea or satiety early during exenatide treatment may predict and/or explain weight loss response. We will assess hunger, nausea and satiety at each study visit using standard 10cm horizontal visual analog scales.

**Physical activity monitoring with Actigraph accelerometers:** Subjects may be given wrist-worn accelerometers (Actigraph, MiniMitter) at week 0 to measure baseline physical activity levels. The will allow us to compare and control for baseline physical activity level differences between the placebo and exenatide groups. Subjects may be asked to wear the monitors again at study week 12, at study week 24, and after achieving 5%, 10%, 15%, weight loss, or weight loss > 15% at a 5% increment.

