## B2. SIGNIFICANCE AND BACKGROUND FOR THE STUDY

Incretin mimetics, medications that mimic the effects of incretin hormones produced by the L cells of the small intestine, are gaining popularity for the treatment of type 2 diabetes. Incretin mimetics are typically associated with more weight loss than any other class of antidiabetic agents. Exenatide, a glucagon-like peptide 1 (GLP-1) receptor agonist, was the first incretin mimetic approved in 2005. Liraglutide, a GLP-1 analog, was approved in 2010, and there are several additional incretin mimetics in development. Exenatide causes glucose dependent insulin secretion, restoration of the first phase insulin response, and reduction of postprandial glucagon secretion. Exenatide also causes delayed gastric emptying and decreases food intake through mechanisms that are not completely understood (Drucker et al., 2003; Iltz et al., 2006; Palamara et al., 2006). Exenatide is currently approved as a twice daily injection.

Exenatide is associated with weight loss among individuals with type 2 diabetes when used as monotherapy or in conjunction with metformin or a sulfonylurea (Buse 2004; DeFronzo 2005; Kendall 2005; Riddle 2006; Moretto 2008; Buse 2009). Exenatide and liraglutide have also been associated with weight loss among obese individuals without diabetes (Rosenstock 2010; Astrup 2010). Retrospective analysis has shown that weight loss is greater among diabetic individuals with BMI > 30 compared to those with BMI < 30, however there are no published prospective studies that have characterized individuals who have robust weight loss with exenatide. Similarly, there are no studies that have examined weight trajectories following termination of exenatide treatment among individuals without diabetes.

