*Physical activity monitoring with actigraph watches:* If the device is available, subjects will be given actigraph monitors at week 0 to measure baseline physical activity levels. The will allow us to compare and control for baseline physical activity level differences between the placebo and exenatide groups. Subjects will be asked to wear the monitors again at week 12, at week 24, and after achieving 5%, 10%, 15%, and > 15% weight loss.

*Thermic effect of food:* Immediately after the mixed meal is consumed, subjects will remain supine for 4 hours while energy expenditure is measured using indirect calorimetry. Resting energy expenditure will be measured for 15-20 minutes every hour for four hours in a subset of subjects. Blood will be drawn between these REE measurements.

*Laboratory studies:*

- Analysis of the CBC, standard chemistries, lipid panel, transaminases (AST and ALT), lipase, TSH, and hemoglobin A1c will be performed at LabCorp.

- Analysis of leptin, insulin, cortisol, adiponectin, and CRP will be performed at the Harvard Catalyst Core Laboratory (HCCL). CRP may be analyzed at LabCorp as well.
- Analysis of soluble leptin receptor and FGF21 will be performed in the laboratory of **[name]** using commercially available ELISA kits.
- Blood will also be banked at enrollment (week 0), week 12, week 24, week 52, 5% weight loss, 10% weight loss, 15% weight loss, and > 15% weight loss in 5% increments for future measurement of incretin levels or other proteins or hormones involved in metabolism. The banked blood may be analyzed in the HCCL, the laboratory of **[name]**, or in collaboration with other researchers.

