To estimate the number and shape of the weight loss trajectories, we will use a mixture modeling technique of the longitudinal data of monthly weights for each subject. We will first plot the data for each subject over time. The graphs will allow us to have some understanding of the shape of the observed trajectories, and how the curves cluster. We will assume that the number of clusters ranges from one to six, but we expect the optimal estimate of the number of clusters is three or four, as described above, with the largest cluster consisting of trajectory of shape T1. The marginal density of a subject having weight measurement at a particular time point is modeled as a function of the product of two densities: the probability of the weight measurement belonging to a particular group, and the probability of observing such a measurement conditioning on the particular group. The first probability is modeled using a generalized logit model since the outcome is categorical (from 1 to 6 categories/types of trajectories), and the second probability is a polynomial linear regression of the weight measurement as a function of time (linear, quadratic, cubic). To select the optimal number of trajectories, we will compare the Bayesian Information Criteria (BIC) value from the six models (corresponding to 1 to 6 types of trajectories). The algorithm and the SAS macro for this type of modeling has been published (Jones 2007). We will repeat the modeling technique above for group B in order to assess the number and shapes of the trajectories in this group.

For aim 2, we will first create a binary outcome variable. The outcome is 1 if the weight loss difference between 12-week and 52-week is at least 1 kg; otherwise, it is 0. We will perform multivariable logistic regression to assess the association between metabolic parameters and this outcome. We consider the association to be statistically significant if the p-value is less than 0.05, and the overall model c-statistic is above 0.8. Once these metabolic parameters have been identified and quantified, we will also use the result from the trajectory analysis (aim 1) to assess the distribution of the metabolic parameters across different trajectories. We will model the likelihood of falling into a particular trajectory as a function of metabolic parameters (i.e. the change in a particular metabolic parameter may affect a certain trajectory but not all trajectories of weight loss).

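### The aim-2 logistic and trajectory-membership models specify no adjustment for body size, so a marker that only tracks size may be taken for a predictor of weight change

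*Combined protocol and SAP*

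**What the plan says.** The aim-2 outcome is in absolute kilograms: "The outcome is 1 if the weight loss difference between 12-week and 52-week is at least 1 kg; otherwise, it is 0". The model is given in one sentence: "We will perform multivariable logistic regression to assess the association between metabolic parameters and this outcome". The decision rule has two parts: "We consider the association to be statistically significant if the p-value is less than 0.05, and the overall model c-statistic is above 0.8". No covariate list follows. The same section then models the probability of belonging to each trajectory class as a function of metabolic parameters, and repeats the models in the diet group (group B). The classes themselves come from polynomial regressions of monthly weight on time, with one to six classes compared by BIC.

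The metabolic parameters are not defined in that section. The serum panel under Outcome measurements reads: "Subjects will have blood drawn to measure leptin, soluble leptin receptor, insulin, cortisol, adiponectin, CRP, and FGF21". Body size appears elsewhere, but not in these models. Outcome measurements plans a separate analysis, "Weight loss will be correlated to baseline BMI", and observes that "Baseline body composition may predict response to exenatide treatment". The one baseline factor for which adjustment is planned is activity, with monitors intended to "compare and control for baseline physical activity level differences between the placebo and exenatide groups". Weight, BMI and impedance body composition are all collected.

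**The concern.** Leptin and insulin are linked to adiposity, and the inclusion criteria admit BMI 28 to 50. If body size is related to the outcome and is left out of the model, a marker that merely stands in for size can look like a predictor. The secondary objective is to find metabolic characteristics that predict a robust response. An unadjusted coefficient cannot tell a hormonal signal from a bathroom-scale reading.

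The plan gives some reason to expect a link between size and loss: "Retrospective analysis has shown that weight loss is greater among diabetic individuals with BMI > 30 compared to those with BMI < 30". The trajectory step raises the problem more directly. Classes formed from raw weight can separate women by how heavy they are rather than by how their weight changes.

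**Working it through.** **Inputs from the document.** Analysed numbers 38 (group A) and 18 (group B), SD of the week 12-52 change 1.2 kg and difference 1 kg (Sample size calculation); the 1 kg threshold and the p<0.05 and c>0.8 rule (Statistical methods); seven serum markers (Outcome measurements); BMI 28-50 (Inclusion Criteria).

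**Assumptions not in the document.** Height 1.63 m; BMI mean 37, SD 5 or 7; mean week 12-52 loss 1.1% (SD 1.3%); marker-weight correlation 0.5-0.8; two-sided tests.

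**1. The plan's own figure.** The plan gives no operating figure for aim 2. Its power statement does reproduce: SE = 1.2 × √(1/38 + 1/18) = 0.343; 1/0.343 − 1.96 = 0.95; Φ(0.95) = 0.83, as stated. The simulated SDs of kg loss in step 4 (1.19-1.31) are close to the plan's 1.2.

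**2. Scale alone.** If percent loss is unrelated to weight W, P(loss ≥ 1 kg) = 1 − Φ((100/W − 1.1)/1.3).
- W = 70 kg: 1 − Φ(0.25) = 0.40.
- W = 130 kg: 1 − Φ(−0.25) = 0.60.

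That is a shallow gradient across the whole entry range (28 × 1.63² = 74 kg to 50 × 1.63² = 133 kg), because 1 kg is close to no change.

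**3. Logistic model, assumed correlations.** The marker acts only through weight, half the women have outcome 1, and there are 2,000 trials per setting. Share reaching p<0.05 without weight in the model:

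| Marker-weight r | Weight-change r | n=38 | n=50 |
|---|---|---|---|
| 0.6 | 0.3 | 11.7% | 15.1% |
| 0.6 | 0.5 | 27.0% | 36.8% |
| 0.8 | 0.3 | 17.3% | 22.3% |
| 0.8 | 0.5 | 47.6% | 59.6% |

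With weight added: 3.7-4.2% (n=38) and 3.7-4.6% (n=50). When c>0.8 is also required at n=38, about 1-8% pass with a single marker and about 10-33% with seven. The gate weakens in the second case because seven markers overfit 38 women.

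**4. Logistic model, scaled to the plan.** n=38, 4,000 runs per setting, leptin-weight correlation 0.5-0.7, the other six markers pure noise:

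| Correlation of kg loss with weight | Leptin alone, p<0.05 | In 7-marker model, p<0.05 | 7 markers, p<0.05 and c>0.8 | p<0.05 with weight added (leptin alone; 7 markers) |
|---|---|---|---|---|
| 0.12-0.15 (scale only) | 5-6% | 6-8% | 4-5% | 4%; 5-6% |
| about 0.42 | 13-27% | 15-27% | 10-20% | 4%; 5-6% |
| about 0.6 | 26-51% | 26-49% | 18-38% | 3-4%; 4% |

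Changing only the outcome, to a loss of at least 1.1%, gives about 4% in the first row but 8-36% in the other two. A percent outcome does not replace adjustment.

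**5. Trajectory step.** At 1.63 m, a BMI SD of 5 is 5 × 1.63² = 13.3 kg and an SD of 7 is 18.6 kg. Either is more than ten times the 1.2 kg SD of change, so a mixture fitted to raw weight is driven by level. This was simulated for 38 women with percent loss unrelated to weight, 0.5 kg within-woman noise, and one to six quadratic classes chosen by BIC (200 runs per setting). The classes explained 96-97% of the variance in starting weight. A leptin with no effect of its own differed across classes at p<0.05 in 65-69% of runs (correlation with weight 0.5) and in at least 99% (correlation 0.7). Analysis of variance across assigned classes stood in for the membership model.

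**The case against.** The best case for the plan has five parts.

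- **Silence is not exclusion.** The model is called multivariable, its covariates are not listed, and the investigators clearly had body size in view. This stands: adjustment is unspecified, not ruled out. But an unlisted covariate leaves the choice open until the data are seen.
- **Scale is harmless.** A reader might infer that heavier women losing more kilograms is enough to produce a false predictor. Step 4 shows it is not; the rate stays near nominal.
- **The p<0.05 rate is not the plan's rule.** A reader might take 12-48% as the rate of false declarations. The rule also requires c>0.8, which cuts the rate sharply for one marker and much less for seven.
- **The supporting evidence is thin.** The BMI comparison is retrospective and in diabetic patients, who are excluded here, and it does not concern change after week 12 in women already selected for 5% loss. The remark in B2 that a fall in leptin may mirror weight loss is about change in a marker, which starting weight does not address. Both points stand. The document makes a link between size and loss plausible but does not show one for this population.
- **The comparison of groups A and B.** A reader might infer that comparing coefficients must carry the same confounding into the claimed exenatide effect. The document does not support that. If weight acts alike in both arms, the bias is common and largely cancels. In a simulation with 38 and 18 women, the coefficient difference was significant in about 3.5% of runs, with a median near zero. Bias there would need a weight relation that differs by arm.

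On the trajectories, it can be said that the plan talks of patterns of loss and of slopes. The quantity it writes into the model, however, is the weight measurement itself.

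**Conclusion.** The concern holds in a limited form. Neither model specifies adjustment for body size. In the logistic model the harm is conditional on heavier women also losing a larger share of weight. Under the correlations in step 3, and judged by the plan's full rule, a marker that only tracks size would pass in roughly 1-8% of trials if tested alone and 10-33% in a seven-marker model. These correlations are assumptions, and nothing in the document fixes them. If scale is the only link, there is no material problem.

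The trajectory step is the stronger case. It does not need heavier women to lose proportionally more, only that classes are fitted to raw weight as written and that the marker is correlated with weight. This is a change that should be made, but it does not undermine the trial.

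**What to change.** In Statistical methods:

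1. Add week-12 (or week-0) weight or BMI as a fixed covariate in the aim-2 logistic models for both groups, and name the choice in advance. Call a parameter a predictor only on the adjusted estimate, and keep the c>0.8 rule. A percent-loss outcome can serve as a sensitivity analysis.
2. Fit the trajectories to weight change from week 12, in kg or percent, instead of raw weight, and include weight in the membership model where class sizes allow. Adding weight while the classes still rest on raw weight would risk near-separation.
3. Describe group B coefficients as descriptive, since about 18 women can support few covariates.

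The cost is slightly wider intervals for markers that track weight closely, one extra coefficient in each logistic model, and up to five (6 − 1) in a six-class membership model. No new data are needed.

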### *Expected attrition rate:*

We expect a 20-25% attrition rate based on the literature and our experience with our initial study. We plan to enroll an additional 50 subjects to account for this expected attrition rate.

**Sample size calculation:**

Based on published literature describing weight loss with exenatide treatment among individuals with type 2 diabetes, we hypothesize that responders will stratify into a plateau group and a continued weight loss group by 52 weeks of treatment. The sample size is based on the difference between two differences of weight. The first difference is the weight difference between week 12 and week 52 for the exenatide group (group A), and the second difference is the difference between week 12 and week 52 for the diet-induced group (group B). The difference in weight loss between these two groups is hypothesized to be 1 kg (i.e. the exenatide group between week 12 and 52 loses on the average 1 kg more than group B). The common standard deviation of the distribution of the weight loss difference is 1.2 kg. We plan to enroll 150 subjects in group A and 36 in group B. Given an expected dropout rate of 25% from the screening visit, we will screen 200 for group A, and 50 for group B. At 12 weeks, we expect that 30% of group A will be high responders (50 subjects). At 52 weeks, we expect the dropout rate to be 25% for group A and 50% for group B. Thus we will have 38 subjects left for group A, and 18 for group B for final data analysis. Given this sample size, we will still have a power of 0.83 to detect the difference of 1kg.

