##### Rationale for study design:

Subjects are randomized to exenatide treatment with general dietary counseling or placebo treatment with aggressive dietary intervention. We are including placebo treatment with aggressive dietary intervention in order to minimize potentially unequal dropout rates in the exenatide versus dietary intervention arms. We will not be able to achieve our primary objectives without an adequate control group that loses at least 5% of body weight with dietary intervention alone.

As of 7/1/14, using a 3:1 randomization scheme, we have enrolled 84 subjects in the exenatide group and 28 in placebo. Due to a higher-than-expected exenatide high responder rate (approximately 60% compared to our prediction of 30%), we must change our randomization scheme to 1:1 to enroll enough subjects in the placebo group for comparison. The number of subjects screened will also be increased from 250 to 300 to achieve our enrollment goal of 250. Thus, we will screen 148 more subjects for a total of 300 screened.

As of 6/5/15, using a 1:1 randomization scheme, we enrolled 24 subjects in the exenatide group and 10 in placebo. Due to a higher than expected drop out rate in the exenatide group and a high response rate in the placebo group, we will change our randomization scheme to 2:1 to enroll enough subjects in both groups for comparison based on our original power calculation. The following figure outlines the new changes:

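### The sample size section miscounts group A (30% of 150 is 45, not 50), and its inputs no longer match the design described elsewhere; the effect on power is small

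*Combined protocol and SAP*

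**What the plan says.** Section B3.B, Sample size calculation, sets out this sequence:

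- Enrolment: "We plan to enroll 150 subjects in group A and 36 in group B".
- Screening: "Given an expected dropout rate of 25% from the screening visit", 200 are to be screened for group A and 50 for group B.
- Response in group A: "At 12 weeks, we expect that 30% of group A will be high responders (50 subjects").
- Attrition: "At 52 weeks, we expect the dropout rate to be 25% for group A and 50% for group B".
- Analysis set: "Thus we will have 38 subjects left for group A, and 18 for group B for final data analysis".
- Power: "Given this sample size, we will still have a power of 0.83 to detect the difference of 1kg". The assumed common standard deviation is 1.2 kg. Neither alpha nor the test is stated.

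The Expected attrition rate section adds 50 subjects to cover attrition of 20-25%, without naming the base to which they are added.

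Section B3.A, Rationale for study design, describes a trial that has moved on. It reports "As of 7/1/14, using a 3:1 randomization scheme, we have enrolled 84 subjects in the exenatide group and 28 in placebo", and an exenatide high-responder rate of "approximately 60% compared to our prediction of 30" per cent. Allocation then went to 1:1, and 24 and 10 were enrolled under that scheme. It is now 2:1, which the Overview and the Recruiting and randomization section also give. The reasons offered for 2:1 are more exenatide dropout than anticipated and a high placebo response, and the stated aim is to satisfy the original power calculation. The same section gives an enrolment goal of 250, with 300 to be screened.

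**The concern.** This is the only power statement for the comparison of groups A and B on weight change from week 12 to week 52, and the plan still points to it when justifying the current allocation. Two things are wrong with it as written. One count does not follow from its own percentage, and the error passes into the number of completers used for power. In addition, its response rate, allocation and enrolment total are not those of the trial described in the design sections. A reader working from this paragraph cannot get from the stated inputs to the stated analysis set, nor tell what power the current design is expected to have.

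**Working it through.** **Inputs.** From Sample size calculation: difference 1 kg, SD 1.2 kg, 150 and 36 enrolled, 30% response in A, dropout 25% (A) and 50% (B). From Rationale for study design: about 60% response, goal of 250 enrolled from 300 screened. Assumed: two-sided alpha of 0.05. The 0.05 given under Statistical methods belongs to the logistic regression, but two-sided 5% is what reproduces the plan's figure; one-sided 5% would give 0.90.

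**Step 1: the plan's own figure.** Normal approximation: power = Φ(δ / (σ√(1/nA + 1/nB)) − 1.96).

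- 38 v 18: standard error = 1.2 × √(1/38 + 1/18) = 0.343; 1/0.343 = 2.91; Φ(2.91 − 1.96) = 0.830.
- The noncentral t gives 0.816.

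So 0.83 is a correct calculation for 38 v 18.

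**Step 2: the counts.**

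- 200 × 0.75 = 150. Agrees.
- 50 × 0.75 = 37.5, against 36 printed. Close.
- 150 × 0.30 = 45, against 50 printed. A count of 50 needs 50/150 = 33.3%. Taking 30% of the 200 screened does not rescue it either, as that is 60.
- 45 × 0.75 = 33.75, about 34, against 38 printed. The 38 is 50 × 0.75 = 37.5 rounded up, so this is the same slip carried forward and not a second one.
- 36 × 0.50 = 18. Agrees.

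**Step 3: power under each count** (1 kg, SD 1.2 kg, two-sided 5%).

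| Completers A v B | Basis | Normal | t | Detectable difference at 80% power (t) |
|---|---|---|---|---|
| 38 v 18 | as printed | 0.830 | 0.816 | 0.98 kg |
| 34 v 18 | 30% of 150, less 25% | 0.816 | 0.801 | 1.00 kg |
| 68 v 18 | 60% of 150, less 25% (67.5) | 0.88 | 0.87 | 0.90 kg |

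The slip costs about 1.5 percentage points. It costs little because group B contributes most of the variance: (1/18)/(1/38 + 1/18) = 0.0556/0.0819 = 68%.

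**Step 4: inputs against current text.**

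| Item | Sample size calculation | Design sections |
|---|---|---|
| Response in A | 30% | about 60% observed |
| Allocation A:B | 150:36 = 4.2:1 | 3:1, then 1:1, now 2:1 |
| Enrolled | 150 + 36 = 186 | goal 250 |
| Screened | 200 + 50 = 250 | 300 |

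The additional 50 subjects do not close the enrolment gap: 186 + 50 = 236, not 250. At the sample size section's own 75% yield, 300 screened gives 300 × 0.75 = 225 enrolled, also below 250.

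**The case against.** The best defence is that this is one slip with almost no consequence. Every other link in the sequence holds or nearly does, 0.83 is right for 38 v 18, and power stays at about 0.80 with the count corrected. The design rationale also openly labels the calculation as original, calls 30% a prediction, and reports the observed 60% beside it. A calculation made at the design stage could not have used rates seen later, and 30% turned out to be conservative. What carries forward to the 2:1 decision may be simply the target of 38 v 18, which does not depend on the faulty step. The design figures are not reproduced in the text available and may contain updated counts.

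Most of that stands and fixes the weight of the point. It does not remove the count error, and it does not make the totals of 186 and 250 agree. Nor does it supply a power figure for the present allocation, when the rationale itself says that exenatide dropout exceeded expectation.

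Three stronger readings are tempting and are not supported.

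- **The trial is underpowered.** The one update with a number attached raises power. With 150 × 0.60 = 90 responders, dropout after week 12 would have to exceed 1 − 38/90 = 58% before group A fell below 38. Actual dropout is not given, so neither a loss nor a gain can be asserted for the current design.
- **The 18 in group B is wrong because placebo subjects are removed at weeks 12 and 24.** The 50% dropout can naturally be read as including those removals, and the documents do not say otherwise. The rationale reports a high placebo response. If the 10 placebo subjects enrolled under 1:1 are additional to the first 28, then 38 are already enrolled against 36 planned.
- **The enrolment goal needs an implausible screening yield.** One can derive 300 − 148 = 152 screened, 112/152 = 74% enrolled, and 138/148 = 93% needed from then on. That assumes every one of the 152 had been resolved by 7/1/14, which the documents do not state. The comparison of 225 with 250 at the plan's own yield needs no such assumption.

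**Conclusion.** The concern holds as a minor error of arithmetic and consistency. On the section's own inputs, group A should have 45 high responders and about 34 completers. Power is then 0.82 (normal) or 0.80 (t) in place of 0.83 or 0.82, assuming a two-sided 5% level. The response rate, allocation and enrolment total in that section also differ from current text elsewhere in the protocol.

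It would be wrong to conclude that 0.83 was miscalculated or that power has been lost. The first reproduces, and the second is not shown. The 0.88 (normal) or 0.87 (t) at 60% response keeps the other planned inputs, including 25% dropout in A and 18 completers in B, so it is an indication and not a forecast. Confidence is high for the count and for the textual mismatches.

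**What to change.** Revise the sample size section as follows:

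1. Make the rate and counts agree: 45 and 34 at 30%, or state the 33% rate that gives 50 and 38.
2. Restate power for the corrected counts, naming alpha, sidedness and the test.
3. Add a recalculation using the observed response and dropout rates and the actual allocation (84:28 under 3:1, 24:10 under 1:1, then 2:1), saying whether the 24 and 10 are additional to the earlier counts.
4. Reconcile the enrolment totals of 186 and 250 across Rationale for study design, Expected attrition rate and Sample size calculation, stating the base for the additional 50 and whether 250 means enrolled or screened.

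The cost is rewording in these sections and a short calculation from data the investigators already hold. It adds no patients or visits, and the restated power may turn out higher than 0.83.
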